8.3.2 Neuroanatomy/Neuronal architecture

#A skin biopsy samples will be investigated for epidermal neuroanatomy/neuronal architecture. Briefly, the PFA-fixed part of the biopsies will be used to analyze the epidermal nerve fiber density and anatomy. Nerve fibers will be visualized by staining consecutive sections for the pan-axonal marker protein gene product 9.5 (PGP9.5); the basement membrane will be visualized by staining for collagen type 4 in order to determine exactly the point of invasion of nerve fibers into the epidermis.

Quantification of intraepidermal nerve fiber density will be calculated by assessing nerve fibers crossing the basement membrane per square millimetre (F/mm²).

Branching of epidermal nerve fibers will be assessed semi-quantitatively by classifying patients into 4 groups comprised of only linear, mainly linear, mainly branched or only branched fibers.

8.3.3 Reverse transcription quantitative PCR (qRT-PCR)

#B skin biopsy samples will be investigated by qRT-PCR for a panel of epidermal neuro- and inflammatory markers including (corresponding gene IDs provided in brackets):

- NK-1R (*TACR1*)
- MRGPRX1 (*MRGPRX1*)
- MRGPRX2 (*MRGPRX2*)
- MRGPRX4 (*MRGPRX4*)
- TRPV1 (*TRPV1*)

- TRPA1 (*TRPA1*)
- Periostin (*POSTN*)
- Integrin alpha 6 (*ITGA6*)
- Anoctamin -1 (*ANO1*)
- TRKA (*NTRK1*)
- Neurturin (*NRTN*)
- IL-4 (*IL4*)
- IL-13 (*IL13*)
- IL-31 (*IL31*)

8.3.4 RNA in situ hybridization (ISH)

#C skin biopsy samples will be investigated by ISH for a panel of epidermal neuro- and inflammatory markers including (corresponding gene IDs provided in brackets):

- MRGPRX1 (*MRGPRX1*)
- MRGPRX2 (*MRGPRX2*)
- MRGPRX4 (*MRGPRX4*)
- TRPV1 (*TRPV1*)
- TRPA1 (*TRPA1*)
- NK-1R (*TACR1*)

8.3.5 Immunohistochemistry (IHC)

#C skin biopsy samples will be investigated by IHC for a panel of epidermal neuro- and inflammatory markers including

- NGF
- NK-1R
- TRPV1
- TRPA1
- SEMA3A
- Integrin alpha 6
- Periostin

These markers will be co-localized with cell type markers for mastocytes, basophils, eosinophils, macrophages, lymphocytes, and keratinocytes.

8.3.6 Nanostring-digital spatial profiling (N-DSP)

#D skin biopsy samples will be investigated by N-DSP for a broad panel of RNA and protein targets.

The purpose of this study is to characterize the neuroinflammatory response to dupilumab treatment in participants with AD. The GeoMx™ digital spatial profiling is a commercial technology that allows for the analysis *in situ* of up to 1,833 immune genes and 92 immune protein targets simultaneously in their tissue-based morphological context from formalin fixed paraffin embedded or fresh frozen samples (18, 19). This technology will allow us to study the spatial association of nerves and immune cells in the skin and deeply profile their phenotypes and signalling pathways throughout the course of treatment. Specific RNA and protein expression targets will be selected to identify key inflammatory cells implicated in AD pathogenesis, such as lymphocytes, eosinophils, mast cells, and macrophages; inflammatory cytokines such as IL-4, IL-5, IL-9, IL-13; signalling pathways such as NK-κB and JAK-STAT; and neuromediators and their receptors, such as histamine, proteases, opioid receptors, neurotrophins, and sodium channels. The target gene and protein list will provide a comprehensive assessment with unprecedented resolution of the effect of dupilumab on inflammatory processes in lesional tissue.

8.4 SAFETY ASSESSMENTS

Planned time points for all safety assessments are provided in the SoA ([Section 1.3](#) and [Section 1.4](#)).

8.4.1 Physical examinations

- A complete physical examination will include, at a minimum, assessments of the skin, cardiovascular, respiratory, and neurological systems. Height and weight will also be measured and recorded.
- Signs and symptoms of hypersensitivity reaction (if any) will be documented.
- A skin focused physical examination will be performed prior to each skin biopsy assessments at time points according to SoA ([Section 1.3](#) and [Section 1.4](#)).
- Investigators should pay special attention to clinical signs related to previous serious illnesses.
- Any new finding or worsening of previous finding should be reported as a new AE.

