8.5.7 Disease-related events and/or disease-related outcomes not qualifying as AEs or SAEs

Not applicable.

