10.3.1 Definition of AE

AE definition

- An AE is any untoward medical occurrence in a patient or clinical study participant, temporally associated with the use of study intervention, whether or not considered related to the study intervention.
- NOTE: An AE can therefore be any unfavorable and unintended sign (including an abnormal laboratory finding), symptom, or disease (new or exacerbated) temporally associated with the use of study intervention.

Events meeting the AE definition

- Any abnormal laboratory test results (hematology, clinical chemistry, or urinalysis) or other safety assessments (eg, ECG, radiological scans, vital signs measurements), including those that worsen from baseline, considered clinically significant in the medical and scientific judgment of the Investigator (ie, not related to progression of underlying disease), eg:
 - Symptomatic and/or
 - Requiring either corrective treatment or consultation, and/or
 - Leading to IMP discontinuation or modification of dosing, and/or
 - Fulfilling a seriousness criterion, and/or
 - Defined as an AESI.
- Exacerbation of a chronic or intermittent pre-existing condition including either an increase in frequency and/or intensity of the condition.
- New conditions detected or diagnosed after study intervention administration even though it may have been present before the start of the study.
- Signs, symptoms, or the clinical sequelae of a suspected drug-drug interaction.
- Signs, symptoms, or the clinical sequelae of a suspected overdose of either study intervention or a concomitant medication.
- “Lack of efficacy” or “failure of expected pharmacological action” per se will not be reported as an AE or SAE. Such instances will be captured in the efficacy assessments. However, the signs, symptoms, and/or clinical sequelae resulting from lack of efficacy will be reported as AE or SAE if they fulfil the definition of an AE or SAE.
- The signs, symptoms, and/or clinical sequelae resulting from lack of efficacy will be reported as AE or SAE if they fulfil the definition of an AE or SAE. Also, “lack of efficacy” or “failure of expected pharmacological action” also constitutes an AE or SAE.

Events NOT meeting the AE definition

- Any clinically significant abnormal laboratory findings or other abnormal safety assessments which are associated with the underlying disease, unless judged by the Investigator to be more severe than expected for the participant's condition.

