- The disease/disorder being studied or expected progression, signs, or symptoms of the disease/disorder being studied, unless more severe than expected for the participant's condition.
- Medical or surgical procedure (eg, endoscopy, appendectomy): the condition that leads to the procedure is the AE.
- Situations in which an untoward medical occurrence did not occur (social and/or convenience admission to a hospital).
- Anticipated day-to-day fluctuations of pre-existing disease(s) or condition(s) present or detected at the start of the study that do not worsen.

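### Protocol Section 8.4.1 and Section 10.3.1 give sites different rules for when a worsened examination finding is an adverse event, 10.3.1 is itself inconsistent, and nothing says which rule prevails

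*Protocol*

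**What the plan says.** Protocol Section 8.4.1 covers the complete examination, with skin first among the systems named, and a skin-focused examination before each biopsy. Its last bullet reads: "Any new finding or worsening of previous finding should be reported as a new AE". It sets no threshold, makes no exception for eczema and does not refer to Appendix 3.

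Protocol Section 10.3.1 (in Appendix 3) contains four statements that bear on the same finding:

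- Abnormal test results and other safety assessments are AEs when abnormal, "including those that worsen from baseline, considered clinically significant in the medical and scientific judgment of the Investigator".
- Not AEs: "other abnormal safety assessments which are associated with the underlying disease, unless judged by the Investigator to be more severe than expected".
- Also not AEs: "expected progression, signs, or symptoms of the disease/disorder being studied, unless more severe than expected".
- Yet listed as an AE: "Exacerbation of a chronic or intermittent pre-existing condition including either an increase in frequency and/or intensity of the condition".

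The same section has two adjoining bullets on lack of efficacy. The first says it is not in itself reported as an AE or SAE. The second says it is one.

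Protocol Section 8.5.7, headed "Disease-related events and/or disease-related outcomes not qualifying as AEs or SAEs", is marked as not applicable and has no other content. Section 8.5 makes investigators responsible for recording events that meet the AE definition, and Section 8.5.2 sends recording and evaluation to Appendix 3. Neither mentions 8.4.1.

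Incidence of treatment-emergent AEs (TEAEs) is the only safety endpoint in Protocol Table 1. SAP Section 1.2.7.1 states that clinical significance of examination findings is not held in the database.

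**The concern.** Consider an area of eczema that looks worse at a skin examination but is within what one expects of the disease. Under 8.4.1 it is an AE. Under the exclusions in 10.3.1 it is not. Under the exacerbation bullet in 10.3.1 it is again. Two sites can each follow the protocol and record different things.

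This matters because AE incidence is the study's safety result for patients, and it comes from a single treated arm of 34 at 2 to 4 centres (Protocol Sections 5 and 6.3). There is no comparator arm of patients in which the same reporting habit would appear and cancel. If centres differ in practice, the difference cannot be separated from a difference between centres. The published percentage would then partly reflect the reporting rule. Section 10.3.2 adds that an event that is not an AE cannot be an SAE, so the classification can also carry over to serious-event reporting.

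**Working it through.** The plan gives no figure to reproduce, so the check is mainly textual. The arithmetic only sets a scale.

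**Step 1: one finding, each rule.** Take ordinary worsening of eczema at a skin examination, not judged clinically significant and not beyond expectation.

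| Source | Is it an AE? |
|---|---|
| 8.4.1, last bullet | Yes |
| 10.3.1, abnormal safety assessments | No |
| 10.3.1, exclusion of disease-associated assessments | No |
| 10.3.1, exclusion of the disease being studied | No |
| 10.3.1, exacerbation of a pre-existing condition | Yes |
| 8.5.7 | Silent |

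Physical examination is not among the examples of safety assessments in 10.3.1, but Section 8.4 classes it as one, so the significance test reaches it. That test applies to abnormal tests and assessments. The general AE definition at the head of 10.3.1 has no such test.

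**Step 2: does anything rank the rules?** Sections 8.5 and 8.5.2 point to the AE definition and Appendix 3, but do not make 8.4.1 subject to them. The SAP adds no rule.

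**Step 3: when can it happen?** As extracted, the schedule in Protocol Section 1.3 places the physical examination at Screening, Day 1 and Week 21. Skin-focused examinations precede biopsies: Day 1 and Week 17 are mandatory, Weeks 3 and 21 optional. Section 9.4.8.1.1 closes the TEAE period at the end-of-treatment visit (Week 17, included). The examinations that can feed TEAEs are therefore mainly the skin-focused ones at Week 17 and, if that biopsy is taken, Week 3. Week 21 findings mostly go to the separate summary of AEs outside the treatment-emergent period (Section 9.4.8.1.2), unless onset is dated earlier.

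**Step 4: scale.** One reclassified participant moves incidence by 1/34 = 2.9 percentage points.

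Let q be the share of participants with a finding that is an AE only under 8.4.1, and p the share who have another AE anyway, the two being independent. If all sites follow one rule rather than the other, incidence shifts by (1 − p) × q. Neither input is in the documents; both ranges are assumptions.

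| | p = 30% | p = 50% | p = 70% |
|---|---|---|---|
| q = 5% | 3.5 | 2.5 | 1.5 |
| q = 10% | 7.0 | 5.0 | 3.0 |
| q = 20% | 14.0 | 10.0 | 6.0 |

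(percentage points)

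The extremes are (1 − 0.70) × 0.05 = 1.5 points, or 0.5 of 34 participants, and (1 − 0.30) × 0.20 = 14 points, or 4.8 of 34. For comparison, the normal-approximation 95% margin for a proportion of 50% at n = 34 is 1.96 × √(0.25/34) = 16.8 points.

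**Step 5: can it be undone later?** Not from the examination data, since clinical significance is not recorded. In part from the AE data, since AEs are MedDRA-coded (Protocol Section 9.4.8.1.1, SAP Section 1.1) and atopic dermatitis terms can be set apart.

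**The case against.** The strongest reply is that Sections 8.5 and 8.5.2 already supply a route: a finding is recorded only if it meets the definition in Appendix 3. That is a sensible reading, but the text does not state it, and it would not give one answer because 10.3.1 points both ways on worsened eczema. This weakens the conflict between 8.4.1 and 10.3.1 without removing it.

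Several objections limit the point, and they stand:

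- A reader might take 10.3.1 as the plain opposite of 8.4.1. The exacerbation bullet rules that out.
- A reader might infer from 8.5.7 that no disease-related event is exempt from AE reporting. Its entry can equally mean that no category is defined beyond Appendix 3.
- A reader might expect worsened eczema to be common because topical treatment is stopped. The documents give no rate. Section 6.5.2 bars topical treatment from at least 4 weeks before Screening, so early washout effects should already be in the baseline, and Section 2.3.3 expects benefit.
- A reader might imagine a very large effect, say 12 of 34 participants (35.3 points). That needs an unsupported rate, no other AE in any of those participants, and all sites on one rule set against all sites on the other.
- A reader might expect the examination after treatment has ended to drive TEAE incidence. Week 21 falls after the TEAE window.

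It can also be said that TEAEs are already tabulated by preferred term and all AEs listed, so dermatitis terms will be visible. True, but a table by term does not give the number of participants with any AE once those terms are removed. That eczema worsening may appear both in AE tables and in EASI or SCORAD is not an error, since safety and efficacy are reported separately.

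**Conclusion.** The contradiction is on the face of the Protocol: one unqualified rule in 8.4.1, a narrower one in 10.3.1, further disagreement within 10.3.1, and no statement of precedence. Recorded AE incidence for worsened eczema can depend on the section a site follows, and the examination data will not allow this to be corrected afterwards.

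The size cannot be derived from the documents. It is 2.9 points per reclassified participant, and 1.5 to 14 points under the stated assumptions on p and q, their independence, and uniform practice across sites under each rule. Within the TEAE window the exposure is limited mainly to the skin-focused examinations at Week 17 and optionally Week 3. This is a problem of consistent safety reporting in a descriptive study. It does not touch the primary endpoints. It is worth correcting because the affected quantity is the only safety endpoint and the correction is small.

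**What to change.** 1. Reconcile Protocol Sections 8.4.1, 8.5.7 and 10.3.1 so that one AE-reporting rule applies to worsening of the studied disease. Within 10.3.1, this means settling the exacerbation bullet against the disease-under-study exclusion, and the two lack-of-efficacy bullets against each other. Section 8.4.1 should then cross-refer to that rule. A cross-reference to 10.3.1 as it stands would leave the conflict in place.
2. In Protocol Section 9.4.8.1.2 and the SAP, report TEAE incidence and post-treatment AE incidence with and without atopic dermatitis preferred terms, with the list of terms fixed before database lock.

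The cost is a small wording amendment, which needs IRB/IEC approval under Protocol Section 10.1.1, and one extra line in the AE tables. The table line needs no new data and can be added even if it is too late for the wording to change collection. It would not resolve findings other than eczema that differ only on clinical significance; for those, only the wording change helps.

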8.4.2 Vital signs

Vital signs will be measured for AD participants in a semi-supine position after 5 minutes rest and will include heart rate, body temperature (°C), systolic and diastolic blood pressure (mmHg).

8.4.3 Pregnancy testing/Postmenopausal females

Pregnancy testing will be performed for all female AD participants of childbearing potential. Urine pregnancy (β -HCG) testing will be performed at time points according to SoA ([Section 1.3](#)). In case of positive urine test the study treatment will be withheld and a serum pregnancy test should be performed as soon as possible, to confirm the pregnancy.

Women will be tested for their FSH concentration in blood in case their postmenopausal status is not confirmed otherwise.

8.5 ADVERSE EVENTS AND SERIOUS ADVERSE EVENTS

Adverse event will be reported by the participant (or, when appropriate, by a caregiver, surrogate, or the participant's legally authorized representative).

The Investigator and any qualified designees are responsible for detecting, documenting, and recording events that meet the definition of an AE or SAE and remain responsible for following up AEs that are serious, considered related to the study intervention or study procedures, or that caused the participant to discontinue the study intervention (see [Section 7](#)).

8.5.1 Time period and frequency for collecting AE and SAE information

All SAEs will be collected from the signing of the ICF until the follow-up visit at the time points specified in the SoA ([Section 1.3](#) and [Section 1.4](#)).

All AEs will be collected from the signing of the ICF at the time points specified in the SoA ([Section 1.3](#) and [Section 1.4](#)).

All SAEs and adverse event of special interest (AESI) will be recorded and reported to the Sponsor or designee immediately and under no circumstance should this exceed 24 hours, as indicated in Appendix 3 ([Section 10.3](#)). The Investigator will submit any updated SAE data to the Sponsor within 24 hours of it being available.

Investigators are not obligated to actively seek AE or SAE after conclusion of the study participation. However, if the Investigator learns of any SAE, including a death, at any time after a participant has been discharged from the study, and he/she considers the event to be reasonably related to the study intervention or study participation, the Investigator must promptly notify the Sponsor.

8.5.2 Method of detecting AEs and SAEs

The method of recording, evaluating, and assessing causality of AE and SAE and the procedures for completing and transmitting SAE reports are provided in Appendix 3 ([Section 10.3](#)).

Care will be taken not to introduce bias when detecting AEs and/or SAEs. Open-ended and non-leading verbal questioning of the participant is the preferred method to inquire about AE occurrences.

8.5.3 Follow-up of AEs and SAEs

After the initial AE/AESI/SAE report, the Investigator is required to proactively follow each participant at subsequent visits/contacts. At the pre-specified study end-date, all SAEs and AEs of special interest (as defined in [Section 8.5.6](#)), will be followed until resolution, stabilization, the event is otherwise explained, or the participant is lost to follow-up (as defined in [Section 7.3](#)). Further information on follow-up procedures is provided in Appendix 3 ([Section 10.3](#)).

8.5.4 Regulatory reporting requirements for SAEs

- Prompt notification by the Investigator to the Sponsor of a SAE is essential so that legal obligations and ethical responsibilities towards the safety of participants and the safety of a study intervention under clinical investigation are met.
- The Sponsor has a legal responsibility to notify both the local regulatory authority and other regulatory agencies about the safety of a study intervention under clinical investigation. The Sponsor will comply with country-specific regulatory requirements relating to safety reporting to the regulatory authority, Institutional Review Boards (IRB)/Independent Ethics Committees (IEC), and Investigators.
- Serious adverse events that are considered expected will be specified in the reference safety information (IB).
- Investigator safety reports must be prepared for suspected unexpected serious adverse reactions (SUSARs) according to local regulatory requirements and Sponsor policy and forwarded to Investigators as necessary.
- An Investigator who receives an Investigator safety report describing a SAE, SUSAR, or any other specific safety information (eg, summary or listing of SAEs) from the Sponsor will review and then file it along with the IB and will notify the IRB/IEC, if appropriate according to local requirements. It is the responsibility of the Sponsor to assess whether an event meets the criteria for a SUSAR, and therefore, is expedited to regulatory authorities.

8.5.5 Pregnancy

- Details of all pregnancies in female AD participants will be collected after the start of study intervention and until 12 weeks after EoS Visit.
- If a pregnancy is reported, the Investigator should inform the Sponsor within 24 hours of learning of the pregnancy and should follow the procedures outlined in Appendix 4 ([Section 10.4](#)).
- Abnormal pregnancy outcomes (eg, spontaneous abortion, fetal death, stillbirth, congenital anomalies, ectopic pregnancy) are considered SAEs.

8.5.6 Cardiovascular and death events

Not applicable.

8.5.7 Disease-related events and/or disease-related outcomes not qualifying as AEs or SAEs

Not applicable.

8.5.8 Adverse event of special interest (AD participants only)

An AESI is an AE (serious or nonserious) of scientific and medical concern specific to the Sponsor's product or program, for which ongoing monitoring and immediate notification by the Investigator to the Sponsor is required. Such events may require further investigation in order to characterize and understand them. Adverse events of special interest may be added, modified or removed during a study by protocol amendment.

The following events are AESIs and require reporting to the Sponsor within 24 hours of learning of the event:

- Anaphylactic reactions.
- Systemic hypersensitivity reactions.
- Helminthic infections.
- Any severe type of conjunctivitis or blepharitis.
- Keratitis.
- Clinically symptomatic eosinophilia (or eosinophilia associated with clinical symptoms).

The following events also require reporting to the Sponsor within 24 hours of learning of the event:

- Pregnancy of a female participant entered in a study as well as pregnancy occurring in a female partner of a male participant entered in a study with IMP;
 - It will be qualified as an SAE only if it fulfills one of the seriousness criteria (see Appendix 3 [[Section 10.3](#)]).
 - In the event of pregnancy in a female participant, IMP should be discontinued.
 - Follow-up of the pregnancy in a female participant or in a female partner of a male participant is mandatory until the outcome has been determined (See Appendix 4 [[Section 10.4](#)]).
 - Abnormal pregnancy outcomes (eg, spontaneous abortion, fetal death, stillbirth, congenital anomalies, ectopic pregnancy) are considered SAEs.
- Symptomatic overdose (serious or nonserious) with IMP.
 - An overdose (accidental or intentional) with the IMP is an event suspected by the Investigator or spontaneously notified by the participant (not based on systematic IMP accountability checks) and defined as at least twice the intended dose within the intended therapeutic interval, adjusted according to the tested drug. The circumstances (ie, accidental or intentional) should be clearly specified in the verbatim and symptoms, if any, entered on separate adverse event forms.

